5.4.4 Research and Training Staff

All proposed study staff have participated in the required trainings in participation and conduct of studies that involve human subjects, and any future study staff will do so upon hiring. Research staff at individual SRVs who interact with participants at assessments do not need to be clinicians. A research assistant (RA) level position should be sufficient to verify eligibility during both study aims, obtain informed consent, be available for questions during the CASI, abstract viral load information via chart reviews, take a blood sample for viral load, control the AI during clinician assisted virtual reality sessions, and explain the Tough Talks intervention. Research staff at SRVs will be trained in person and/or via videoconferencing on the intervention components and will be given a script and checklist to review with participants. If a participant asks a question that study staff do not feel equipped to answer, SRV study staff will contact research staff at the University of North Carolina at Chapel Hill and/or Duke University and then follow up with the participant.

5.4.5 Intervention Monitoring/Quality Control

Because the Tough Talks intervention is an app, intervention fidelity is assured for all activities, except for the virtual reality activities (i.e., all participants will receive the intervention in the same way and have access to all of the same resources). For the virtual reality activities, Arm 1 participants will have the avatar controlled by the AI and Arm 2 participants will have the avatar controlled by staff. However, for both VR activities, the same utterance database is being used so while we anticipate that the staff controlled avatar may perform better, the types of conversations and specifics on what words/phrases can be said in both arms will be the same. To maintain quality control the study team will train and score practice VR scenarios and retrain if needed prior to enrollment visits. The UNC study team will also review the first 10 VR session transcripts performed at each SRV site, and then 20% of the sessions on an ongoing basis. Site staff with issues will be re-trained.

6.0 EVALUATIONS AND MEASURES

THIS SECTION CONTAINS RELEVANT EVALUATIONS AND MEASURES FOR THE RCT ONLY

Overviews of the administration of clinical and behavioral measures are shown in the Schedule of Evaluations with a full list of study measures. Presented below is additional information on visit-specific measure administration and procedures.

6.1 Screening

Online, phone-based, and in-person screeners will be used to determine if individuals meet initial eligibility criteria. Individuals may be screened for eligibility by accessing the study's online screener using their own laptop or mobile device (e.g., if responding to online or community recruitment) or may complete the online screener on a local clinic tablet or computer. The online screener may also be administered by study staff to potential participants in person or over the phone. All potential technical pilot participants who meet the initial eligibility criteria (based on the screener) must arrange an in-person enrollment visit to confirm eligibility. Potentially eligible RCT participants can select an online visit if needed. Eligibility will be confirmed at the enrollment visit based on the confirmation of screener completion in past 30 days, and VL measure within the past year of screener completion (or up until the enrollment visit date).

6.1.1 Administrative and Behavioral Procedures

- Screening assessment, in-person, by phone, or online

6.2 Enrollment

Participants must be scheduled for an enrollment visit within 30 days of online, phone, or in-person screening; otherwise they will need to be re-screened. Individuals who meet initial eligibility criteria

based on the online screener will be scheduled for an enrollment visit, where screener completion, including recent VL measure will be confirmed.

6.2.1 *Administrative and Behavioral Procedures*

- Informed Consent/Assent
- Randomization to Arm 1 (online), Arm 2 (clinic delivery) or Arm 3 (SOC)
- Baseline CASI Assessment
- Introduction and orientation to Tough Talks
- For Arm 1 and Arm 2 participants, unique Tough Talks account creation, download and set up of Tough Talks on participant's mobile device
- For Arm 2 participants, completion of 1st half of Tough Talks program
- Remuneration for enrollment completion (including BL survey)

6.3 Two-Week Follow Up (Arm 2 only)

Participants in the clinic arm (Arm 2) will be scheduled for a two-week follow up to complete the second half of the program. The eligible window for completing the two-week follow up is any time during week 2 to week 4 of their intervention.

6.3.1 *Administrative and Behavioral Procedures*

- Completion of 2nd half of Tough Talks program
- Remuneration for completion

6.4 One-Month Assessment (Immediate Post Intervention)

The intervention will last for 1 month. The 1-month assessment should occur as soon after their 1-month enrollment period as possible. However, given that the one-month assessment is the only one that includes measures of overall intervention acceptability, the assessment may occur up to 160 days after the ideal 1-month assessment time point (e.g. up until the end of follow-up period). SMART will aid study staff in ensuring retention. SMART maintains participant follow-up timelines, tracks participant communications, and automates sending of e-mail, text reminders, and calendar invites to participants for follow-up survey and visit completion. An appointment for the 1-month assessment visit will be scheduled to complete the following procedures listed below.

At one month, all participants will complete an online survey to assess intervention acceptability as well as to assess SCT model constructs. Participants will receive \$25 for completion.

A sub-set of participants (20-30 total) in both intervention arms (10-15 in each arm) will complete a qualitative exit interview to evaluate the program in-depth and document a more nuanced understanding of intervention acceptability and impact. Participants in both interventions will be eligible to participate in an interview after completion of their one-month follow-up survey. The interviews will be conducted in person or online using a HIPAA-compliant, IRB-approved videoconferencing software program. Online interviews will be recorded by the software program and back-up recorded using an

external digital audio recorder. In-person interviews will be recorded using two digital audio recorders. Interviews will last 45-60 minutes and participants will receive an additional \$50 for completing a qualitative exit interview.

6.4.1 Behavioral Evaluations

- One-month CASI assessment
- Qualitative exit interview (for subgroup of participants)
- Remuneration for survey completion
- Updates to contact/locator information

6.5 Three-Month Assessment

A second assessment should occur 90 days (3 months) after study enrollment. However, the assessment may occur 15 days prior to or 30 days after the ideal three-month assessment time point. SMART will aid study staff in ensuring retention. SMART maintains participant follow-up timelines, tracks participant communications, and automates sending of e-mail, text reminders, and calendar invites to participants for follow-up survey and visit completion. At three months, all participants will complete a second online survey and staff will conduct a medical chart abstraction for VL results in the week window surrounding the three-month follow up visit (both before and after). Participants will complete the 3-month follow up survey remotely and will receive \$25 for completion. Payment is not contingent upon having a VL result in the required window. Participants who miss their 1-month follow up are eligible to complete their 3-month visit.

6.5.1 Behavioral Evaluations

- Three-month CASI assessment
- Remuneration for online survey completion

6.5.2 Clinical Procedures

- Viral load measure, taken from chart (if within six weeks prior to or following three-month follow up)

6.6 Six-Month Assessment

The final assessment should be conducted 6 months after study enrollment. However, the assessment may occur two weeks prior to or 30 days after the ideal final assessment time point. At six months, all participants will complete a third online survey and undergo a medical chart review to abstract VL data. If participants have had a viral load taken in the two months prior to their six-month follow up appointment, they can complete the six-month follow-up survey remotely and receive their follow-up incentive. If they do not have a VL result from the prior two months, they can still complete their survey remotely but will be asked to provide a blood sample to assess viral load within three months of completing the six-month survey. Participants will receive \$50 for completion. Participants must complete both their survey and have an eligible viral load (either through chart review in last two months, self-report, or blood sample within three months after survey) to receive their incentive.

Participants who miss their one and/or three-month follow up are eligible to complete their final six-month visit.

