Clinical Samples	Viral load suppression: Viral loads will be assessed through chart review, blood draw, or participant shared documentation at baseline, 3 and 6 months. Participants with no VL result in their medical record in the 2 months prior to or 3 months after their 6-month follow up visit will have one drawn for the study. Participants may also self-report viral load at 6 month. Viral load suppression will be defined as HIV RNA < lower limit of detection as per the laboratory processing the sample.

Phase 2 (RCT) Study Schema

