4.0 SELECTION AND ENROLLMENT OF PARTICIPANTS

4.1 Inclusion Criteria

Inclusion Criteria for All Aims

- Age 16-29 years
- Assigned male sex at birth
- Born male and male-identified
- Able to understand, read, and speak English

Additional Criteria for Technical Pilot:

- Reports ≥ 1 episode of CAI with a male partner in past 6 months
- HIV-positive (self-report)

Additional Criteria for RCT:

- HIV-positive (medical chart review)
- Viral Load measure within 12 months of screening date (assessed by chart review, blood draw, or shared by participant via video teleconferencing or Qualtrics)
- Owns and has reliable access to a smartphone or tablet
- Has reliable internet access
- Reports ≥1 episode of anal sex with a male partner in past 6 months (self-report) OR reports STI diagnosis (urethral/rectal gonorrhea or chlamydia or syphilis) in the last six months (self-report OR medical chart review)

As this is a minimal risk study, we will seek a waiver of parental consent for YMSM under age 18 (see Human Subjects section).

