6.6.1 Administrative and Behavioral Procedures

- Six-month CASI assessment
- Remuneration for visit completion (dependent on both survey and viral load)
- Documentation of viral load measure (blood draw, self-report or chart review)

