6.6.2 Clinical Procedures

- Viral load measure, abstracted from medical chart or blood sample

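### Three places in the protocol accept participant self-report as a six-month viral load, the sections that define and analyse the primary endpoint list only laboratory-sourced results, and nothing says how an undocumented value is treated.

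*Combined protocol and SAP*

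**What the plan says.** **Places that accept self-report at six months**
- Study Abstract, Clinical Samples row: "Participants may also self-report viral load at 6 month". The same row has already said "Viral loads will be assessed through chart review, blood draw, or participant shared documentation at baseline, 3 and 6 months", so self-report is named in addition to shared documentation.
- Section 6.6, on the conditions for the six-month payment: participants must complete the survey and "have an eligible viral load (either through chart review in last two months, self-report, or blood sample within three months after survey".
- Section 6.6.1: "Documentation of viral load measure (blood draw, self-report or chart review".

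Section 5.4.3 adds a related route, values that the participant shares through Qualtrics, without saying whether a laboratory report must be attached.

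**Places that list only laboratory-sourced results**
- Section 2.1 (primary outcome) and Table 2: chart review or study draw.
- Section 6.6.2: "Viral load measure, abstracted from medical chart or blood sample".
- Section 10.3.3 (RCT Primary Analysis Plan): a chart result from the two months before the visit; failing that, a study draw or a routine-care measurement within three months after it.

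**Safeguards already in the text**
- Every chart is reviewed at six months.
- Under the Clinical Samples row, a participant with no result on record in the window "will have one drawn for the study". Under section 6.6, participants without a recent result "will be asked to provide a blood sample to assess viral load within three months of completing the six-month survey".

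Suppression is defined in section 2.1 by the detection limit of the laboratory that processed the sample. Neither section 10.3.3 nor section 10.4 says whether a participant with only an undocumented value is observed or missing.

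**The concern.** The two source lists lead to different data sets for the primary endpoint, and either choice has a cost.

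If undocumented values count, an objective measurement becomes partly a statement by participants who have been told their arm (section 5.4.3). Such a statement may carry no laboratory name, assay limit or sampling date, so neither the detection limit nor the time window could be checked. Over-reporting of suppression at the same rate in all arms shrinks the risk difference. Over-reporting at different rates biases it.

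If they do not count, section 6.6 still lets a self-report earn the payment. That weakens the incentive to give the blood sample requested in the same paragraph.

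Because the text does not settle which applies, the choice could be made after the data have been seen.

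**Working it through.** **Step 1. The sources side by side**

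| Place | Chart | Study draw | Routine care after visit | Shared by participant | Self-report |
|---|---|---|---|---|---|
| Abstract, Clinical Samples | yes | yes | – | yes (documentation) | yes |
| 2.1 | yes | yes | – | – | – |
| 5.4.3 | yes | yes | – | yes (Qualtrics) | – |
| 6.6 (payment) | yes | yes | – | – | yes |
| 6.6.1 | yes | yes | – | – | yes |
| 6.6.2 | yes | yes | – | – | – |
| 10.3.3 | yes | yes | yes | – | – |
| Table 2 | yes | yes | – | – | – |

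Sections 6.6.1 and 6.6.2 are adjacent lists for the same visit and differ.

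**Step 2. The plan's own figure**

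Inputs from section 10.2.3: 0.66 at baseline, 0.88 at six months under intervention, two-sided alpha 0.05, 80% power, 15% loss, 66 per arm. The six-month rate under standard of care is not stated; 0.66 is assumed.

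Pooled two-proportion formula, with mean rate 0.77:

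n = [1.96·√(2·0.77·0.23) + 0.842·√(0.66·0.34 + 0.88·0.12)]² / 0.22² = 56.3, so 57 evaluable per arm.

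57 × 1.15 = 65.6, which rounds up to 66; 57 / 0.85 = 67.1, which rounds up to 68. The stated 66 reproduces closely. With 66 × 0.85 ≈ 56 evaluable per arm, power is 0.798.

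**Step 3. What self-report could do**

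The documents give neither the share f of six-month values that are self-report only nor the probability o that an unsuppressed self-reporter claims suppression. Both are assumptions here.

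(a) *Counted, same error in both arms.* Observed rate p′ = p + f·o·(1 − p), so the risk difference becomes 0.22·(1 − f·o).

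(b) *Counted, error differing between arms, no true effect (0.66 in both).* Bias = f·gap·0.34, where gap is the difference in o between arms. Null SE = √(2·0.66·0.34/56) = 0.0895. Type I error = Φ(−1.96 + bias/SE) + Φ(−1.96 − bias/SE).

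(c) *Excluded.* n = 56·(1 − f·a), where a is the fraction of these cases that come on top of the planned 15% loss.

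| Scenario | f = 5% | f = 20% (illustration only) |
|---|---|---|
| (a) power, o = 0.25 / 0.50 / 0.75 | 0.791 / 0.785 / 0.778 | 0.770 / 0.741 / 0.709 |
| (a) risk difference at o = 0.50 | 0.2145 | 0.198 |
| (b) bias, gap 0.20 / 0.50 | 0.0034 / 0.0085 | 0.0136 / 0.0340 |
| (b) type I error, gap 0.20 / 0.50 | 5.0% / 5.1% | 5.3% / 6.7% |
| (c) power, a = 1 / 0.5 / 0 | 0.777 / 0.788 / 0.798 | 0.703 / 0.754 / 0.798 |

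At 5% nothing moves materially. At 20%, counting the values with o = 0.50 gives 74% power, and excluding them gives 70% to 80%. The figures do not show whether lost power or bias would dominate.

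**The case against.** The strongest reply is that the endpoint source is already settled. Sections 2.1 and 10.3.3 and Table 2 name their sources positively, and section 10.3.3 gives an ordered rule. The word eligible in section 6.6 governs payment, and section 6.6.1 is an administrative list. This largely stands: it is the most natural reading of those sections. It does not close the gap, because the Clinical Samples row places self-report beside the definition of suppression and no sentence excludes it.

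Second, self-report may simply mean a shared laboratory report. Section 4.1 describes an eligibility value "assessed by chart review, blood draw, or shared by participant via video teleconferencing or Qualtrics", and section 6.6.1 speaks of documentation. That is possible, but the Clinical Samples row lists shared documentation separately and then adds self-report.

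Third, no share or error rate can be taken from the documents. Charts are reviewed for everyone, blood is requested, and payment depends on having a value, not on being suppressed. All of this stands, so the 20% column predicts nothing. In the other direction, section 4.3 lets remote participants take part entirely online, which could make the share larger among them.

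Fourth, the power figures do not favour exclusion over acceptance. That also stands. The case for documented results rests on being able to apply the endpoint's own definition and window, not on power.

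A reader might infer that the plan has decided to use undocumented statements in the primary analysis, or that the primary result will be materially biased. The documents support neither: the analysis section names only laboratory-sourced values, and nothing indicates how many self-reports there would be or how accurate.

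**Conclusion.** The conflict between source lists is real and concerns the primary endpoint. The sections that define and analyse it lean towards laboratory results only, the Clinical Samples row pulls the other way, and the treatment of an undocumented value is unstated. It should be resolved before outcome data are examined.

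Its numerical size cannot be established. At an assumed 5% share it is negligible. At 20% power could fall to between 70% and 77%, depending on how the values are handled, or type I error could rise to between 5.3% and 6.7%, but only under assumed error rates and between-arm gaps that the documents do not supply. All figures also assume 0.66 as the six-month rate under standard of care and 56 evaluable per arm. The stated sample size is not called into question. Confidence is moderate, mainly because self-report may have been meant as a shared laboratory report.

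**What to change.** 1. Reconcile the Clinical Samples row, sections 2.1, 5.4.3, 6.6, 6.6.1, 6.6.2 and 10.3.3, and Table 2 to one list of eligible six-month sources: a chart or routine-care result in the stated window, a dated laboratory report shared by the participant, or the study draw already planned.
2. Define self-report, and say whether it includes a shared report.
3. Record the source of each value on the CRF and report it by arm.
4. In section 10.3.3, count only documented laboratory results in the primary endpoint. Treat undocumented values as missing, under the plan's missing-endpoint method fixed in advance, and use them only in a labelled sensitivity analysis.
5. Align the payment wording in section 6.6 with the list.

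The cost is protocol and SAP wording plus one CRF field. The downside is an unknown number of additional document requests, draws or missing endpoints, mainly among remote participants, with some possible loss of power. Section 11.3.1 already allows draws at an independent laboratory, which may ease part of that burden. The remote share is not given, so the number cannot be estimated from the documents.

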6.6.1 Administrative and Behavioral Procedures

- Six-month CASI assessment
- Remuneration for visit completion (dependent on both survey and viral load)
- Documentation of viral load measure (blood draw, self-report or chart review)

6.6.2 Clinical Procedures

- Viral load measure, abstracted from medical chart or blood sample

6.6.3. Laboratory Procedures

- Blood specimen analysis for viral load (if not in chart review)

7.0 DATA COLLECTION AND SITE MONITORING

7.1 Development of Protocol and Case Report Forms

The protocol team is responsible for the development of this protocol as well as the Case Report Forms (CRFs) needed to collect the information required to implement this protocol. All Case Report Forms are input in REDCap, where study staff will complete all relevant fields.

7.2 Data Records

Participant-related study information will be identified through a study ID number (SID) and participant code on all participant CRFs, audio files, transcripts, and CASI files. Participant names or other personally-identifying information will not be used on any study documents other than the Contact Information Worksheet (stored in double-locked office separate from other study information only accessible by designated study staff) and informed consent form and will be redacted from usability and field trial interview transcripts. All study-related information will be kept in double-locked, limited access areas at each study site. Participant names and their SID and participant code will be stored in SMART Web, accessible only to designated study staff, and representatives from the NICHD. SIDs will not be entered into the mobile app and instead a unique app ID will be assigned to each participant and used when setting up the app. These unique App IDs will be provided by the UNC Study Team and recorded into the Intervention Delivery Form during enrollment. Original source documents (e.g., Contact Information Worksheet) for individual participants will be maintained at the respective SRV and will be accessible only to the study staff. Data from original source documents will be transcribed with SMART or on CRFs in REDCap as applicable. Electronic data will be stored on a secure server at UNC.

7.3 Data Collection

7.3.1 CRFs

Study monitoring data, including information about eligibility, demographic data, and monitoring untoward effects will be collected on CRFs. All CRFs for this study must be entered into REDCap. Hard copies will be made available for download from a UNC-run secure cloud management platform, to be used if needed (i.e. technical issues preventing use of REDCap).

7.3.2 CASI Survey Data

Technical Pilot: Self-administered surveys will be completed by participants at the baseline and 1-month assessment time points. Participants will complete an online computer assisted self-interview (CASI) via survey hosts on Qualtrics.

RCT: Self-administered surveys will be completed by participants at the baseline, 1-month, 3-month and 6-month assessment time points. Participants will complete an online computer assisted self-interview (CASI) via survey hosts on Qualtrics.

Data collected using a CASI method at the clinic sites will be entered on a portable computer or mobile phone via an internet-based application. All data collected using CASI will remain confidential; no personal identifying information will be collected during the computer session. The participant's unique SID number will be used in order to link the interview responses to the participant's CRF data. This unique SID will also be used to link participant completed follow-up Qualtrics surveys

